## **COVER PAGE**

# Title of study: Music distraction and its influence on anesthetic requirements during elective knee surgery

NCT number: not yet assigned

Date of document: March 26, 2018

Research investigators: [name], [name], [name], [name], [name]

Hypothesis: music distraction can be used to reduce or eliminate anesthetic requirements when total knee replacement is performed under spinal anesthesia.

#### Specific aims of the study:

- To use music in a way that distracts participants without distracting other health care workers in the operating room
- To use music in a way that does not disrupt the workflow of the anesthesia team or affect their ability to monitor the participant and administer medications safely
- To determine if the music can be used to reduce anesthetic requirements when total knee replacement is performed under spinal anesthesia

## Background:

Music during surgical procedures has been shown to have a number of desirable effects. A review of the literature reveals the following:

- Patients have decreased anxiety, heart rate and blood pressure when music is played for them before and during awake craniotomy(1).
- Patients have decreased pain scores and increased satisfaction when they listen to music under general anesthesia(2).
- Burn patients who listen to music during treatment procedures have decreased anxiety and heart rate(3).
- Surgeons have decreased anxiety when music is played in the procedural suite during cutaneous dermatologic procedures(4).
- Patients have decreased sufentanil opioid requirement when music is played before and after lung resection surgery(5).

To date, there are no studies that assess music and its effect on anesthetic requirements during major elective orthopedic surgery. Spinal anesthesia allows knee and hip surgery to be performed without putting a patient completely to sleep. However, some anesthesia medications are often required as a standard of care to provide patient comfort and reduce patient anxiety. Risks are associated with the use of anesthetic medications, even if the medications are used only for sedation and comfort. These risks include respiratory depression or aspiration of gastric content into the lungs. Occasionally, the aforementioned outcomes result in hospital admission to the intensive care unit. This study has significance because it seeks to explore a non-pharmacologic modality that could ultimately decrease the incidence of complications associated with anesthesia.

#### Methods:

This prospective study will assess music and its ability to influence anesthetic requirements in patients receiving primary elective knee replacement surgery. All research participants will undergo the same surgical procedure by the same surgeon, who is one of the research investigators ([name]).

Potential participants will be recruited during any of three pre-operative encounters that are considered standard to our institution: 1) the surgery clinic visit, 2) the pre-operative anesthesia clinic visit, or 3) the pre-operative surgical unit on the day of surgery. Formal consent will be obtained in the pre-operative surgical unit on the day of surgery.

Prior to surgery, patient participants will receive a combined spinal-epidural per VCU total joint protocol; the following steps are considered standard of care and not considered study procedures. The combined spinal-epidural procedure creates complete numbness below the abdomen down to the feet, which negates the need for general anesthesia. For patient comfort during the combined-spinal epidural procedure, a one-time dose of 2 milligrams of intravenous midazolam will be given; this dose is adequate for reducing anxiety while allowing the patient to maintain conversation with health care providers if necessary. The standard intrathecal dose for total knee replacement at our institution is 15 mg bupivacaine and 0.2 mg preservative-free morphine; this dose will provide complete numbness to the lower extremities for approximately 3-6 hours. After this dose is administered, the patient will then be positioned appropriately in the operating room and vital signs will monitored per standard protocol.

Each patient participant will be randomized to one of two groups. Participants in the control group will receive noise-cancelling wireless headphones that will not play any noise throughout the procedure. Participants in the experimental group will receive the same noise-cancelling wireless headphones but will be permitted to listen to the music of their choice while in the operating room. Music will be provided via Spotify, which is an Internet streaming music service, and will be played through headphones; this way, no other individual in the operating room will be distracted or influenced by the patient's music selection. Participants will not be able to change the Spotify channel. We will be using the paid Spotify service with no commercials. If participants opt to have the music stopped, we will withdraw them from the study and continue standard of care. The participants will have the music playing for about two hours. If the participant has no music preference, the music will be chosen for them and it will be the same for all participants that have no preference. The volume will be adjusted in the operating room until the participant approves of the volume by saying "yes, the volume is good" or giving another verbal cue of approval. The music will continue playing until the surgical procedure is complete and the patient has reached the post-anesthesia recovery unit.

As stated previously, spinal anesthesia provides numbness that negates the need for general anesthesia, but patients often times need additional sedation, which will be defined as anesthesia medication that is

used to treat patient anxiety and discomfort in the operating room. Patient participants in both groups will receive sedation via the same protocol, which is outlined below.

It is important to note that the standard of care for this procedure involves the administration of sedation that is given at the anesthesiologist's discretion; sedation is generally given when the patient exhibits signs of discomfort or anxiety. The protocol described below is designed specifically for this study in order to provide standardization within the study participants; the protocol instructions fall within the standard of care for the administration of sedation by an anesthesia provider.

Sedation will only be given as needed per patient request; the patient will be given a noise-making device (such as a rubber duckie that makes sound when squeezed) that will inform the anesthesia provider that the patient is uncomfortable and needs some sedation. A weight based dose of 0.3 micrograms per kilogram of intravenous propofol will be given for each patient request. This dose is expected to provide amnesia or light sleep for a few minutes. For patient safety, if the patient requests sedation more than once within a two minute window, the anesthesia provider will not administer any more medication during this two minute period. Additionally, the anesthesia provider may withhold sedation if he or she determines with physical exam and hemodynamic monitors that the patient is already over-sedated.

After five propofol boluses have been given to a patient, a propofol continuous infusion will be initiated at 25mcg/kg/min. The patient may still request additional sedation with the request instrument if he or she is still conscious enough to do so. If the anesthesia provider has given more than five boluses even with the baseline propofol infusion, the infusion will be increased to 50mcg/kg/min. In the highly unlikely scenario that five additional boluses are required with a propofol infusion rate of 50 mcg/kg/min, the anesthesia providers and investigators will make a clinical decision as to what is the safest next step.

There may be scenarios that warrant conversion to general anesthesia. These scenarios include, but are not limited to, hemodynamic instability, regurgitation of gastric content, obtundation, excessive agitation, and inadequate spinal anesthesia. The decision to convert to the general anesthesia will be made by the anesthesiologist and anesthesia provider in the operating room; implementation of this study should not prevent or delay this decision if it is necessary.

Documentation will be completed by the anesthesia provider per standard protocol for electronic anesthesia charting at VCU. This will allow for data acquisition by the investigators through the anesthesiology printed record in Cerner. The primary outcome for this study will be the amount of sedation required during the surgical procedure; this will be calculated into micrograms of propofol per kilogram per minute. For this study, propofol will be used during the surgical procedure and intravenous midazolam and intrathecal morphine will be used for the spinal procedure; no other sedating

medications will be used. The secondary outcomes for this study will include pain scores and patient satisfaction at determined time intervals before and after the surgery.

Primary data elements that will be obtained are as follows: 1) the total amount of propofol given, 2) the duration of operating room time, which will be defined as "in the operating room" time to "out of the operating room" time. Data will be entered into a spreadsheet; the amount of propofol per unit of time will be calculated by dividing #2 from #1; if there is a difference and it is statistically significant, then our hypothesis is true.

Secondary data elements will include numerical pain scores, which are taken via standard of care nursing assessment immediately after surgery and every four hours afterwards; the study will collect the numerical pain scores that describe each four hour interval for a 24 hour time period. The numerical pain scores will be collected through the patient's medical record after the 24 hour time period has passed. Data will placed into a spreadsheet and a statistical analysis will be performed for each time interval. This will answer the question of whether or not post-operative pain scores are affected the music intervention.

Another secondary data element will include patient satisfaction, which will be determined through a hospital survey that is completed by the patient and is standard of care. The data points will focus on two patient satisfaction questions on the survey, which ask "did you feel like your pain was controlled" and "did you feel like the doctors did everything that could to control your pain." These are yes/no questions, and data can be collected and presented as the percentage of participants that answered "yes" to these questions. As standard of care, the surveys are completed when the patient is discharged from the hospital, the survey data is scanned into the electronic medical record; therefore, this data will need to be collected in the medical record after the participant has completed their hospital stay. This will answer the question of whether or not the music intervention affects patient satisfaction with respect to pain management, which is the area of interest for the study team.

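### Stopping the music counts as leaving the study, a post-randomisation exit open only to the music arm, so the propofol comparison can be biased by selection

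*Protocol*

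**What the plan says.** All of this stands in the Methods of the protocol.

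- Allocation: "Each patient participant will be randomized to one of two groups".
- Control arm: "Participants in the control group will receive noise-cancelling wireless headphones that will not play any noise throughout the procedure". The music arm wears the same headphones with music playing.
- Once the music has been set up: "Participants will not be able to change the Spotify channel".
- If the music is unwanted: "If participants opt to have the music stopped, we will withdraw them from the study and continue standard of care".
- Sedation, which drives the primary outcome: "Patient participants in both groups will receive sedation via the same protocol, which is outlined below", and then "Sedation will only be given as needed per patient request". Usual care is described differently, as "sedation that is given at the anesthesiologist's discretion".
- Source of the propofol and time data: the anesthesia chart, of which the protocol says "This will allow for data acquisition by the investigators through the anesthesiology printed record in Cerner".

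The primary outcome is propofol per kilogram per minute of operating-room time. The hypothesis is declared true if the difference is statistically significant.

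**The concern.** The rule treats two events as one: a participant no longer wants the music, and a participant leaves the study. The first is non-adherence to the assigned intervention. The second removes a randomised person.

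Only one arm can lose people this way. A control participant has no music to stop, and no matching rule covers someone who dislikes or removes silent headphones.

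A link with the outcome is plausible, because propofol is given when a patient signals discomfort. Anxious or uncomfortable participants may ask for the music to stop, and they would also request more propofol. The opposite is equally possible: alert participants with little need for sedation may tire of a channel they cannot change, while heavy requesters may be too drowsy to ask. The protocol does not settle which dominates.

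At stake is the one comparison on which the trial's conclusion rests. A spurious reduction or a spurious increase could arise, and the protocol provides no follow-up of the withdrawn participants from which to tell.

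**Working it through.** The protocol states no sample size, significance level, stop rate or standard deviation, so there is no figure of its own to reproduce. Everything numerical below is an illustration under stated assumptions.

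**1. Who can trigger the rule.** Music arm: yes. Control arm: no. The rule acts after randomisation.

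**2. Size of the bias, closed form.** Assume no true effect. Split participants into thirds by sedation need. One extreme third stops with probability p_h, the other two thirds with probability p_o, and w = (p_h + 2p_o)/3 is the fraction withdrawn. Let m be the mean propofol of the extreme third relative to the overall mean. The relative bias in the remaining music-arm mean is

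-(p_h - p_o)(m - 1) / [3(1 - w)].

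Assumed outcome: 25% need no propofol, the rest are lognormal with CV 0.8, so sigma = sqrt(ln(1 + 0.8²)) = 0.703.

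- Highest third: the top 0.333/0.75 = 44.4% of propofol users, normal cut-point 0.140. Its share of all propofol is Φ(0.703 - 0.140) = 0.713, so m = 3 × 0.713 = 2.14.
- Lowest third: all non-users plus the lowest 0.083/0.75 = 11.1% of users, cut-point -1.221. Its share is Φ(-1.221 - 0.703) = 0.027, so m = 0.08.

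With p_h = 3p_o:

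- w = 5%: p_o = 3%, p_h = 9%; factor 0.06/2.85 = 0.021. Bias -2.4% (highest third stops more) or +1.9% (lowest third).
- w = 10%: p_o = 6%, p_h = 18%; factor 0.12/2.70 = 0.044. Bias -5.1% or +4.1%.
- w = 20%: p_o = 12%, p_h = 36%; factor 0.24/2.40 = 0.10. Bias -11.4% or +9.2%.

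**3. Simulation for false-positive rates.** Same outcome model, Welch t test at two-sided 5%, 10,000 trials per cell, n per arm = 30 / 50 / 100:

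| Withdrawn | Who stops more | Bias in mean | False result in that direction |
|---|---|---|---|
| 0% | – | none | favourable 2.1 / 2.1 / 2.2%; unfavourable 2.3 / 2.5 / 2.4% |
| 10% | highest third, 3:1 | -4.8 / -4.6 / -4.7% | favourable 3.7 / 4.2 / 5.2% |
| 10% | lowest third, 3:1 | +4.1 / +3.8 / +3.8% | unfavourable 3.1 / 3.8 / 4.0% |
| 20% | highest third, 3:1 | -9.6 / -10.1 / -10.0% | favourable 5.5 / 7.6 / 10.5% |
| 20% | lowest third, 3:1 | +7.8 / +7.8 / +8.1% | unfavourable 4.0 / 4.8 / 6.7% |
| 10–20% | unrelated to need | -0.3 to 0.0% | – |

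The simulated bias is slightly smaller than the closed form. If a fixed number is withdrawn by draws weighted 3:1, the realised stop ratio falls below 3. At 20% it is about 34.1% against 13.0%, which gives 0.211/2.40 × 1.14 = 10.0% and 0.211/2.40 × 0.92 = 8.1%, in line with the table.

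**4. A second model, to see whether the shape matters.** Take propofol as standard normal, and remove a music-arm participant when a latent stopping tendency, correlated rho with propofol, exceeds c = z(1 - w). With λ = φ(c)/(1 - w), the bias is -rho·λ and the variance is 1 - rho²·λ(c + λ). For w = 10% and rho = 0.5: c = 1.282, λ = 0.195, bias = -0.097 SD, variance = 0.928. With 50 per arm, SE = sqrt(1/50 + 0.928/45) = 0.202, and the two-sided error is Φ(-1.96 + 0.48) + Φ(-1.96 - 0.48) = 0.077. At rho = 0.3 and 0.8 it is 0.059 and 0.126. At rho = 0 the bias is 0 and the error 0.05. A negative rho reverses the sign. The pattern is the same as in the first model.

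**5. Sedation after a stop.** Study sedation is on patient request only, in both groups. A participant whose music is stopped goes to standard of care, which the protocol describes as discretionary sedation. Whether request-only dosing continues after a stop is therefore unclear, and it affects how the primary outcome is generated.

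**The case against.** Four points can be made for the plan.

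*Exclusion is inferred.* The text withdraws these people but does not say that their data are discarded, and a SAP could define an analysis set by assigned group. This is fair as far as it goes. But the protocol's own rule takes them out of the study and provides for no further collection, and an unseen SAP would not undo it. If the chart can still be read, as is likely, that is a reason to say so in the protocol.

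*The sedation texts may not conflict.* The protocol also says that its sedation instructions lie within the standard of care, and the statement about both groups can be read as covering only people still in the study. That stands: the text is unclear rather than contradictory. The question does become live once these participants are kept in the analysis.

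*The bias may be small.* Participants choose their music and approve the volume, so few may stop. At 5% withdrawn with the highest third stopping more, the bias is between 2% and 3% and the total two-sided error 4.8 to 5.6%. Since the decision rule has no direction, total error matters too: at 10% withdrawn a re-run gave 4.7 / 5.5 / 6.5% (highest third) or 4.9 / 4.6 / 5.7% (lowest third), against 4.6 to 4.8% with no withdrawal. This stands and limits the severity.

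*Dilution is not the only cost of keeping stoppers in.* If sedation becomes discretionary after a stop, propofol could move either way. This also stands, and is why the sedation rule needs reconciling as well.

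**Conclusion.** The concern holds. The protocol fixes a post-randomisation exit that only the music arm can take, for a reason that may be linked to the primary outcome, and nothing in it keeps those participants in the comparison.

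That the rule exists and is one-sided is certain. Its effect is conditional. If stopping is rare or unrelated to need, there is little or no bias. Under the assumed 3:1 selection, 10% withdrawn gives about -5% or +4% in mean propofol, and 20% gives about -10% or +8%. False results in the affected direction rise from about 2% to 3–5% and 4–11% respectively. Stop rate, selection ratio, 30 to 100 per arm and the outcome distribution are all assumptions, and the sign cannot be fixed from the protocol.

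This should be fixed before recruitment: the bias may be modest, but the cure is cheap.

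**What to change.** Replace the withdrawal sentence in the Methods with:

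> *A participant may have the music stopped at any time; this is not withdrawal from the study. Unless consent for data use is withdrawn, propofol, operating-room time, pain and survey data are still collected from the record and analysed in the assigned group.*

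In addition:

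- Record the time of any stop, report the number of stops and the reasons, and tabulate propofol before and after the stop.
- Present a comparison restricted to those who kept the music only as a sensitivity analysis. It drops the same people and does not settle the sedation question.
- The sponsor must reconcile the Methods on which sedation rule applies after the music is stopped, so that the primary outcome is measured the same way in both arms.

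**Cost.** One sentence in the protocol and in the consent text, and one recorded time; the outcome data are already charted. The statistical price is dilution. The share of the true effect retained is 1 - (stop rate × share of effect lost). If stoppers lose half of the music effect, that is 1 - 0.10 × 0.5 = 95% at a 10% stop rate and 1 - 0.20 × 0.5 = 90% at 20%. If they lose all of it, 90% and 80%. These figures assume that sedation follows the same rule before and after the stop.

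### The spoken volume approval in the operating room can occur only in the music arm, so it can disclose the arm to the anesthesia provider, whose decisions partly set the primary outcome

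*Protocol*

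**What the plan says.** All of this is in the Methods section of the protocol.

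- **Headphones, control arm:** "Participants in the control group will receive noise-cancelling wireless headphones that will not play any noise throughout the procedure".
- **Headphones, music arm:** "Participants in the experimental group will receive the same noise-cancelling wireless headphones but will be permitted to listen to the music of their choice" in the operating room.
- **Reason given for headphones:** that "no other individual in the operating room will be distracted or influenced by the patient's music selection". This concerns distraction of staff. Concealment of the arm is not mentioned.
- **Volume:** "The volume will be adjusted in the operating room until the participant approves of the volume by saying" that it is good, or by some other verbal sign of approval. No matching step is described for controls.
- **Sedation:** propofol is given on patient request, with a fixed two-minute lockout during which "the anesthesia provider will not administer any more medication during this two minute period". Apart from the lockout, "the anesthesia provider may withhold sedation if he or she determines with physical exam and hemodynamic monitors that the patient is already over-sedated". An infusion of 25 mcg/kg/min starts once five boluses have been given.
- **Outcome:** the primary outcome is propofol in mcg/kg/min over operating room time. The anesthesia provider does the charting from which the dose is taken.

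**The concern.** Identical headphones, inaudible to others, already provide most of what is needed to keep the anesthesia provider unaware of the arm. The volume step works against this: a participant who approves a volume aloud in the operating room is in the music arm.

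The person most likely to hear it is the one who answers requests. The lockout is objective, but the judgement that a patient is over-sedated is not fully so. The primary outcome is the dose given, not the number of requests made, so it measures patient demand after it has passed through that judgement. If knowledge of the arm shifts the judgement even slightly, the arms can differ in propofol with no difference in demand. The Methods would read a statistically significant difference as confirming the hypothesis. No analysis can restore masking once the step has been carried out.

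**Working it through.** The protocol gives no figure to reproduce here: no sample size, expected difference or withholding rate. The check is a reading of the text, followed by two illustrations.

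**1. Does the step disclose the arm?** Control headphones play nothing, so there is no volume to adjust. No sham check is described. The approval is spoken, and it takes place in the operating room. That it happens in the music arm only is an inference, but a safe one.

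**2. Does the person who may hear it influence the outcome?** Yes, by two routes in the text: discretion to withhold a requested bolus, and an infusion trigger that counts boluses given, not boluses requested.

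**3. How much can one decision move one patient's outcome?** Inputs: bolus 0.3 mcg/kg and infusion 25 mcg/kg/min, both as written, and an assumed 120-minute denominator (the Methods expect about two hours of music). The figures are used as they stand, without comment on the doses.

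Outcome = (boluses × 0.3 + 25 × infusion minutes) / 120

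- One bolus withheld, away from the trigger: 0.3/120 = 0.0025 mcg/kg/min.
- Fifth bolus given at 60 min: (5 × 0.3 + 25 × 60)/120 = 1501.5/120 = 12.51.
- Fifth bolus withheld and none given later: 4 × 0.3/120 = 0.01.
- Fifth bolus given at 30 min: (1.5 + 25 × 90)/120 = 18.76. At 90 min: (1.5 + 25 × 30)/120 = 6.26. Each compares with 0.01 if it is withheld and none follows.
- Trigger delayed by d minutes: 25 × d/120, which is 0.42 for 2 min, 2.08 for 10 min and 4.17 for 20 min.

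On the figures as written, almost all the leverage lies in decisions near the infusion trigger.

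**4. What could this do to a comparison of arms?** This illustration rests on assumptions that the protocol does not supply: a 120-minute stay; a mean of 4 or 8 requests per patient; request rates that vary widely between patients (gamma, shape 1) but have the same distribution in both arms; a two-minute lockout; infusion from the fifth bolus; bolus size varied from 0.3 to 300 mcg/kg to see whether the result depends on it; 30 to 60 patients per arm; and a two-sided 5% rank test.

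| Assumed withholding, arm A vs arm B | Ratio of mean dose, B to A | Rejection rate (nominal 5%) |
|---|---|---|
| 5% vs 15% | 0.85-0.90 (10-15% lower) | about 5-9% |
| 5% vs 25% | 0.67-0.82 (18-33% lower) | about 10-19% |

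The bias is zero if withholding is equal. At the milder contrast the mean is shifted but the error rate is close to nominal. Clear inflation needs a fivefold difference in withholding.

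**The case against.** The strongest reply is that nothing in the protocol is broken. It never says the provider is masked, and the headphones are there to avoid distracting staff, in line with the first specific aim. Discretion is already narrow: a bolus follows a patient request, the dose is weight-based, the lockout is fixed and the infusion steps are count-based. What remains is a safety exception for a patient judged over-sedated on examination and monitors, and that patient has just operated the request device. No withholding rate, and no difference between arms, is documented. Masking would also stay fragile, because a lightly sedated patient may mention the music or ask for it to stop.

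Most of this stands. It limits the likely size of the problem and rules out calling it a contradiction. It does not remove the route: the exception still needs judgement, and imperfect masking elsewhere is no reason to build disclosure into every music-arm case.

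A reader might infer three stronger things that the documents do not support:

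- **That the result will be biased toward the hypothesis.** The text shows only that bias is possible. The direction depends on how a provider who knows the arm would behave, which the protocol does not address.
- **That the volume check lengthens operating room time in the music arm and so lowers its rate.** No duration is given, and the check could run alongside positioning and monitoring. This argument should not be used.
- **That the person who takes consent can do the check.** The Methods say where consent is obtained but not by whom, so it cannot be assumed that someone outside the anesthesia team is available.

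**Conclusion.** The concern holds in a limited form. A spoken step that only the music arm can perform is fixed in the operating room, where it can disclose allocation to the provider who may withhold requested propofol and who charts the primary outcome. Knowledge of the arm can therefore bias that outcome. This is an avoidable design weakness, worth correcting because the correction is cheap. It is not a breach of any stated blinding.

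The size is unknown. The single-patient arithmetic shows that decisions near the infusion trigger carry weight, given the doses as written and a 120-minute denominator. The simulated reductions of 10-15% and 18-33% are illustrations under assumed withholding rates and should not be quoted as expected bias.

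**What to change.** Replace the in-room volume rule with one scripted headphone check used identically in both arms: a short test sound and the same spoken approval. Do it preferably before the participant enters the operating room. If it must be done or repeated in the room, use the same script in both arms. Keep the player screen out of the anesthesia provider's sight, and state in the protocol that the provider is not told the arm.

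It would also help to log every request, and each withheld request with its reason, so that demand can be examined beside dose.

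No sedation rule changes. The cost is a few sentences in the protocol and a small record-keeping task if the log is adopted. The protocol does not say who runs the player; someone other than the provider should do so where possible. The downsides are small: control participants go through a brief sham check, the volume may occasionally need readjusting in the room, and masking stays imperfect because a patient may mention the music or ask to stop it.

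### The propofol bolus of 0.3 micrograms/kg cannot have its stated effect and does not fit the infusion steps that follow it; the figure or its unit is wrong

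*Protocol*

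**What the plan says.** All of the relevant text is in the Protocol, Methods.

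- **Bolus.** "A weight based dose of 0.3 micrograms per kilogram of intravenous propofol will be given for each patient request". The expected effect follows at once: "This dose is expected to provide amnesia or light sleep for a few minutes".
- **Limit on boluses.** For safety, a second request inside a two-minute window is not met, so boluses can come no faster than one every two minutes. The provider may also withhold a dose from a patient who is over-sedated.
- **First infusion step.** "After five propofol boluses have been given to a patient, a propofol continuous infusion will be initiated at 25mcg/kg/min". Requests remain open: "The patient may still request additional sedation with the request instrument if he or she is still conscious enough to do so".
- **Second infusion step.** If boluses go on past five while the infusion is running, "the infusion will be increased to 50mcg/kg/min". Five more boluses at that rate are foreseen, though described as very unlikely.
- **Primary outcome.** Sedation used during the procedure: "this will be calculated into micrograms of propofol per kilogram per minute". It is built from "the total amount of propofol given" and the time in the operating room.

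The bolus dose is stated once, with its unit spelled out in words. The Methods also say that the sedation scheme was written for this study so that participants would be treated in a standard way.

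**The concern.** The bolus and the infusion are the same drug, by the same route, in units that convert directly, and they are steps of one ladder. A bolus said to produce minutes of sleep should be a substantial amount beside an infusion on which a patient may remain awake. As written it is a negligible amount.

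This is an operative dosing instruction. It is the first sedation step for every participant who asks for sedation, and it generates the drug that the primary outcome counts. One of two things follows.

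1. **The dose is given as written.** Uncomfortable patients get almost no drug until the fifth bolus triggers the infusion. Ineffective boluses may also push patients onto continuous sedation that an effective bolus could have spared them, although the Background gives the risks of sedation as the reason for the study. The outcome is coarsened in both arms.
2. **Providers correct the dose themselves.** Delivered doses then depart from the protocol and may differ between providers, which defeats the stated purpose of a common scheme.

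**Working it through.** **Inputs (Protocol, Methods):** bolus 0.3 mcg/kg; at most one bolus per 2 min; infusion 25 mcg/kg/min after five boluses. The milligram column is an inferred alternative that the protocol does not state.

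| Quantity | Formula | As written, 0.3 mcg/kg | If 0.3 mg/kg (300 mcg/kg) |
|---|---|---|---|
| One bolus as time on the first infusion step | bolus / 25 | 0.012 min = 0.72 s | 12 min |
| Five boluses, total | 5 × bolus | 1.5 mcg/kg | 1,500 mcg/kg |
| Five boluses as time on the first infusion step | 5 × bolus / 25 | 0.06 min = 3.6 s | 60 min |
| Fastest bolus rate | bolus / 2 min | 0.15 mcg/kg/min | 150 mcg/kg/min |
| First infusion step relative to that rate | 25 / fastest rate | 167 times | 0.17 times |

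**Further results for the dose as written**

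- One minute of infusion delivers 25/0.3 = 83 boluses' worth, or 25/1.5 = 16.7 times all five boluses together.
- A bolus at every permitted time on top of the infusion adds 0.15/25 = 0.6% to the rate. Yet continued boluses are the trigger for doubling it to 50 mcg/kg/min.
- A patient asking at every permitted time receives the fifth bolus 4 × 2 = 8 minutes after the first, having had 1.5 mcg/kg in all.

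**The contradiction.** If 0.72 seconds' worth of the infusion gives minutes of sleep, a patient could not be expected to stay awake on the infusion itself. If patients can be awake on it and asking for more, the bolus cannot do what is claimed for it. The two-minute safety limit points the same way: at this dose a second bolus would add only another 0.72 seconds' worth of infusion.

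**Effect on the primary outcome under literal dosing.** Operating room time is not stated; the only guide is about two hours of music. I assume 90 to 150 minutes.

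| Assumed operating room time | Five boluses: 1.5 / time | Ten minutes of infusion: 250 / time |
|---|---|---|
| 90 min | 0.017 mcg/kg/min | 2.78 mcg/kg/min |
| 120 min | 0.0125 mcg/kg/min | 2.08 mcg/kg/min |
| 150 min | 0.010 mcg/kg/min | 1.67 mcg/kg/min |

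As an illustration, take five boluses in the first 10 minutes and then 110 minutes at 25 mcg/kg/min (2,750 mcg/kg). The boluses make up 1.5/2,751.5 = 0.05% of the total as written, against 1,500/4,250 = 35% on the milligram reading.

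**The case against.** The arithmetic and the inconsistency are not in dispute. The case on the other side concerns the strength of the reasoning and the size of the harm.

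- **Seconds of infusion measure mass, not effect.** A bolus and an infusion of equal mass need not act alike, so the either/or is an inference and not strict logic. That is right, but the gap is too wide for it to matter: the first minute of infusion alone delivers 83 boluses' worth.
- **The sentence about consciousness is conditional.** Read alone, it also fits a patient who is asleep. The next sentence settles the matter: it provides for boluses beyond five with the infusion running, and boluses are given only on request, so the plan does foresee patients awake on 25 mcg/kg/min.
- **A trained provider would notice.** Probably so; bedside correction is more likely than literal dosing. That is the second consequence and no defence, because the text would then no longer fix the dose. Variation between providers is a possibility, not something the document shows.
- **The outcome survives.** It uses the drug actually given, and both arms share one scheme, so nothing here biases the comparison. This stands. Even under literal dosing the outcome still varies with when the infusion starts, how long it runs and whether it is doubled.
- **The figure errs low, and rescue exists.** Conversion to general anesthesia stays available. This limits the harm of under-dosing but does not correct the figure.

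**Conclusion.** The concern holds, with high confidence, and should be fixed before the first patient. The written bolus is incompatible with its own stated effect and with the infusion ladder: it equals 0.72 seconds of the first infusion step, and boluses at the fastest permitted rate reach 1/167 of that step. These figures come from the protocol alone and need no outside dosing source.

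The consequence for the primary outcome is conditional on literal dosing and on the assumed 90 to 150 minutes in the operating room. The grade rests on this being a wrong drug-dose instruction in the scheme that produces the primary outcome. It does not rest on any claim of bias between arms, and the outcome definition is not at fault.

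**What to change.** Correct the bolus figure or its unit in the sedation paragraph of the Methods so that it agrees with the stated effect and with the 25 and 50 mcg/kg/min steps. The responsible anesthesiologist should confirm the intended dose. Internal consistency points to 0.3 mg/kg (one bolus equal to 12 minutes of the first infusion step, five equal to 60 minutes), but the protocol does not say so and it should not be adopted unconfirmed.

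No other unit needs to change, and the outcome definition stays as it is.

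The cost is a one-line correction with ethics board notification. If the answer is milligrams, the written dose changes 1000-fold; the document does not show whether notification is then enough or approval is needed, so ask the board. Trial size and data collection are unaffected.
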